13.15. Assessment of Efficacy

The primary efficacy objective is based on the ECG data collected as discussed in Section 17.

13.16. Assessment of Safety

The primary safety objective is based on the Adverse Event data collected. Further information on the collection of Adverse Events is discussed in Section 17.

13.17. Recording Data

The study will collect data using Oracle Clinical, an electronic data management system for clinical studies. Centers will enter data onto case report forms (CRFs) within an Oracle Clinical database. The Holter/TTM/12-lead ECG core lab will also enter data onto CRFs within a separate Oracle Clinical database.

Data reported on the CRFs shall be derived from source documents, which may include worksheets, quality of life questionnaires, patient medical records and ECG data. These source documents must be created and maintained by the center personnel. Further detail on data management is provided in Section 19.2.

13.18. Deviation Handling

A study deviation is defined as an event within a study that did not occur according to the CIP or the Clinical Trial Agreement. Prior approval by Medtronic is expected in situations where the Investigator anticipates, contemplates, or makes a conscious decision to deviate. In countries following ISO 14155:2011, prior approval for study deviations will be reported to local authorities and ethics boards per local requirements. If the deviation affects subject's rights, safety and well-being, or the scientific integrity of the study, prior approval from ethics board and/or competent authority is also required, depending on local legislations. Prior approval is not required when a deviation is necessary to protect the safety, rights or well-being of a subject in an emergency or in unforeseen situations beyond the Investigator's control (e.g. subject failure to attend scheduled follow-up visits, inadvertent loss of data due to computer malfunction, inability to perform required procedures due to subject illness). A study deviation is not required if a subject misses a weekly TTM transmission.

For medically justifiable conditions which preempt a subject's ability to complete a study-required procedure, it may be permitted to report only one deviation which will apply to all visits going forward. This may also apply for other unforeseen situations (e.g. the subject permanently refuses to complete a study required procedure and the data will not contribute to the primary endpoint analysis). However, prior approval from Medtronic is required for such situations.

All study deviations must be reported on the eCRF regardless of whether medically justifiable, pre-approved by Medtronic, an inadvertent occurrence, or taken to protect the subject in an emergency. The deviation description must be recorded with an explanation for the deviation.

In the event the deviation involves a failure to obtain a subject's consent, or is made to protect the life or physical well-being of a subject in an emergency, the deviation must be reported to the IRB/MEC as well as Medtronic within five (5) working days. In Japan, the deviation must be immediately reported to Head of Medical Institute (HOMI), to the Ethics Board via the HOMI, and to Medtronic. Reporting of study deviations should comply with IRB/MEC policies, local laws and/or regulatory agency requirements and must be reported to Medtronic as soon as possible upon the center becoming aware of the deviation. Refer to

Investigator Reports, Section 19.5.2, for specific deviation reporting requirements and timeframes for reporting to Medtronic and/or regulatory bodies.

Medtronic is responsible for analyzing deviations, assessing their significance, and identifying any additional corrective and/or preventive actions (e.g. amend the CIP, conduct additional training, and terminate the investigation). Repetitive or serious Investigator compliance issues may result in initiation of a corrective action plan with the Investigator and center, and in some cases, necessitate suspending enrollment until the problem is resolved or ultimately terminating the Investigator's participation in the study. Medtronic will provide center-specific reports to Investigators summarizing information on deviations that occurred at the investigational center on a periodic basis.

13.19. Subject Withdrawal or Discontinuation

A subject can withdraw from the study or the [REDACTED] sub-study at any time. If the subject wishes to exit from the study (i.e. the subject revokes consent), the center is required to document the reason for exit on an eCRF. In addition, centers shall follow the regulations set forth by their IRB/MEC. It is recommended to follow the subject until all ongoing device and/or procedure-related adverse events are resolved or unresolved with no further actions planned. For countries following ISO, permission may be requested to follow-up with the subject outside of the study due to withdrawal based on problems related to the study device safety or performance. Following exit, subjects will continue to receive standard medical care. All data available through the time of the subject's exit will be used for analysis.

Reasons for study exit include:

- Subject lost to follow-up
- Subject did not meet inclusion/exclusion criteria after consent and did not undergo an ablation procedure
- An Arctic Front Advance catheter was not used during the subject's ablation procedure
- Subject did not provide consent or data use protection authorization
- Subject chooses to withdraw (e.g., consent withdrawal, relocation to another geographic location)
- Investigator deems withdrawal necessary (e.g., medically justified, inclusion/exclusion criteria not met, failure of subject to maintain adequate study compliance)
- The sponsor decides the study will be closed or a particular center will be closed

The following information is required to be collected at study exit:

- Reason for exit must be documented on the eCRF and in the subject's medical record

In the case that the subject is determined to be lost to follow-up, details of a minimum of two attempts and the method of attempt (e.g., one letter and one phone record or two letters) to contact the subject must be recorded.

An unscheduled office visit should be attempted if the subject exits the study outside of a scheduled follow-up visit.

14. Risks and Benefits

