The probability of a subject achieving effectiveness success at 12 months (365 days) will be estimated using survival analysis, the Kaplan-Meier method. The standard error will be approximated using Greenwood's formula. A two-sided 95% log-log confidence interval for the probability will be constructed.

For every treated subject, day 0 is defined as the day of the index cryoablation procedure. For subjects with treatment failure, the survival date will be set to the date of the treatment failure. For subjects without treatment failure through 12 months, those subjects will be censored at the last study contact date

Medtronic Confidential

recorded on CRF which may include the last study visit, the exit date, or death date. If a subject without a treatment failure is lost to follow-up, the censoring date will be set to the last known study visit date.

For the component of the endpoint, documented AF/AT/AFL, if this documentation resulted from rhythm monitoring occurring at the 12-month visit within the 12-month visit window, the date of recurrence will be set to 365 days from the study ablation procedure so that these events will be counted as treatment failures in the 12-month Kaplan-Meier analysis.

Performance Requirements

If the lower bound of the 95% confidence interval at 12 months is greater than the performance goal of 40%, the objective will be considered met.

Rationale for Performance Criteria

The choice of twelve month follow-up and acceptable success rate of 40% performance criteria was selected based on the 2012 HRS/EHRA/ECAS Expert Consensus Statement on Catheter and Surgical Ablation of Atrial Fibrillation: Recommendations for Patient Selection, Procedural Techniques, Patient Management and Follow-up, Definitions, Endpoints, and Research Trial Design, provides recommendations for success rates in clinical trials. The recommendation for evaluating the efficacy of a treatment for persistent AF is as follows: *"If minimum chronic success rate is selected as an objective effectiveness endpoint for a clinical trial, we recommend that the minimum chronic acceptable success rate for persistent AF at 12-month follow-up is 40%."*¹

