6.1.3. Analysis Sets

=

The **Full analysis set** consists of all enrolled subjects who sign informed consent. The full analysis set will be used for AE reporting in general and ancillary objective [REDACTED]

The **Modified Intention-to-Treat (mITT)** cohort is the subset of subjects who maintain informed consent at least until the index cryoablation procedure was finished. For endpoints analyzed in this group of subjects, the standard Intention-to-Treat (ITT) protocol applies immediately upon insertion of the cryoballoon catheter into the subject's vasculature. The mITT cohort will be used in the analysis of the primary efficacy objective, the secondary objective regarding Quality of Life (QoL), and the ancillary objective [REDACTED]. The mITT dataset will be used in the analysis of the primary efficacy and safety objectives, as well as for the secondary objective and ancillary objectives [REDACTED].

This study has planned submissions to the US FDA and Japan PMDA. The Pre-Market Approval Submission (PMA-S) to the US FDA will include subjects from centers in US and Canada. If full 12-month data is available from Japan subjects at the time of PMA-S submission, the Japan data may be included in the PMA-S submission. The submission to the Japan PMDA will include analysis from data collected from all four geographies. The analyses for both submissions will follow the same pre-specified analysis procedures, so this SAP will not distinguish between the PMDA submission cohort (165 subjects expected) vs. the subset of subjects used for the PMA-S (150 subjects expected) except when differences due to sample size are relevant to the discussion.

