6.2.2.3. Analysis Methods

The probability of a subject achieving effectiveness success at 12 months (365 days) will be estimated using survival analysis, the Kaplan-Meier method. The standard error will be approximated using Greenwood's formula. A two-sided 95% log-log confidence interval for the probability will be constructed. For every treated subject, day 0 is defined as the day of the index cryoablation procedure. For subjects with treatment failure, the survival date will be set to the date of the treatment failure. For subjects without treatment failure through 12 months, those subjects will be censored at the last study contact date recorded on CRF which may include the last study visit, the exit date, or death date. If a subject without a treatment failure is lost to follow-up, the censoring date will be set to the last known study visit date.

For the component of the endpoint, documented AF/AT/AFL, if this documentation resulted from rhythm monitoring occurring at the 12-month visit within the 12-month visit window, the date of recurrence will be set to 365 days from the study ablation procedure so that these events will be counted as treatment failures in the 12-month Kaplan-Meier analysis. This objective will be analyzed in the mITT dataset: all enrolled subjects who have the Arctic Front Advance Cardiac CryoAblation Catheter inserted into vasculature will be included.

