6.2.2.5. Sensitivity Analyses

A sensitivity analysis will be conducted to estimate the potential impact of subjects with less than 12 months of follow-up at the final analysis, which is described in more detail in section 6.5.

In the event a subject is enrolled, treated, but later discovered they did not meet eligibility, a sensitivity analysis will be conducted to understand the impact of these subjects. The same analysis methods will be utilized as described in section 6.2.2.3, but those subjects not meeting eligibility will be excluded.

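### Protocol 13.19 allows follow-up of already treated subjects to be ended for ineligibility or poor compliance, an avoidable and possibly informative source of censoring

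*Protocol*

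**What the plan says.** **Protocol 13.19** lists the reasons for study exit. One covers ineligible subjects who were never treated: "Subject did not meet inclusion/exclusion criteria after consent and did not undergo an ablation procedure". A separate reason covers withdrawals that the investigator considers necessary. Its examples are medical justification and "inclusion/exclusion criteria not met, failure of subject to maintain adequate study compliance". This second reason is not restricted to untreated subjects. On data use, the section begins "All data available through the time of the" and ends at the subject's exit, so nothing later is used.

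**Censoring.** For subjects without treatment failure, Protocol 17.3.1 states that "those subjects will be censored at the last study contact date". SAP 6.2.2.3 repeats the rule and describes the date as "recorded on CRF which may include the last study visit, the exit date, or death date". The safety analysis uses the same rule (Protocol 17.3.2, SAP 6.2.3.3).

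**Analysis set.** SAP 6.1.3 says that "the standard Intention-to-Treat (ITT) protocol applies immediately upon insertion of the cryoballoon catheter". SAP 6.1.2 excludes for ineligibility only subjects who left before the procedure. SAP 6.2.2.5 removes subjects who were "enrolled, treated, but later discovered they did not meet eligibility" only in a sensitivity analysis. SAP 6.1.1, however, names eligibility as a condition for the primary cohort.

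**The concern.** The study treatment is a single procedure on day 0. After it, withdrawal by the investigator mainly ends observation. The study is single-arm and unblinded, so the person deciding may know or suspect the subject's rhythm. Poor attendance and missed transmissions may themselves be related to recurrence.

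If subjects heading for failure are withdrawn more often than others, censoring is informative and the Kaplan-Meier estimate is biased in favour of the device. The core lab cannot correct this, because it reads only the recordings it receives.

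Safety is exposed as well. Pulmonary vein stenosis and atrio-esophageal fistula count up to 12 months, and phrenic nerve injury counts if unresolved at 12 months.

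**Working it through.** **1. What happens to a treated subject withdrawn for one of the two reasons**

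| Question | Answer | Source |
|---|---|---|
| Still in the analysis set? | Yes, if the catheter was inserted | SAP 6.1.3, 6.2.2.3 (6.1.1 pulls the other way on eligibility) |
| Failure documented before exit? | Counts as a failure | Protocol 17.3.1 |
| Failure-free at exit? | Censored at last contact, which may be exit | Protocol 17.3.1, SAP 6.2.2.3 |
| Rhythm follow-up to 12 months required after exit? | No such requirement found | Protocol 13.19 |

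The tension therefore concerns whether outcomes are ascertained, not who belongs to the set. The sensitivity analysis in SAP 6.2.2.5 is informative only if the primary analysis holds these subjects' 12-month outcomes.

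**2. The plan's own power figure.** Inputs from Protocol 17.3.1: 150 treated, 10% attrition, goal 40%, assumed success 54%, one-sided alpha 0.025, exact binomial. Analysed n = 150 × 0.9 = 135. The smallest r with P(X ≥ r | 0.40) ≤ 0.025 is 66, with actual alpha 0.0224. Power is P(X ≥ 66 | 0.54) = 0.899. This reproduces the stated 90% and the SAP 7.1 table, so the plan's power figures are not in question.

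**3. How few withdrawals move a borderline result.** Assumptions: 150 treated, F true failures all after day 91, w of them censored at day 91, no other attrition. With no censoring between day 91 and day 365, the Kaplan-Meier and Greenwood formulas reduce to:

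- S = (150 − F)/(150 − w)
- G = 1/(150 − F) − 1/(150 − w)
- θ = 1.96 × √G / |ln S|
- lower bound = S^exp(θ)

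For F = 78 (48% true success):

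- w = 0: S = 72/150 = 0.480, G = 1/72 − 1/150 = 0.00722, θ = 0.227, lower bound 39.8%. Goal missed.
- w = 1: S = 72/149 = 0.483, lower bound 40.1%. Goal met.
- w = 3: S = 72/147 = 0.490, G = 1/72 − 1/147 = 0.00709, θ = 0.231, lower bound 40.7%. Goal met.

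For F = 81 (46%), w = 8 moves the lower bound from 37.9% to 40.2%. For F = 69 (the planned 54%), w = 3 gives 81/147 = 55.1% and w = 15 gives 81/135 = 60.0%. The goal is met there with or without withdrawals.

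**4. False-positive rate at a true 40%.** Simulation assumptions: n = 150; 7% of failures acute, 25% at day 365, the rest uniform over days 91–364; log-log lower bound compared with 40%. In the worst case, w would-be failures are each censored one day before documentation. Ranges are over separate runs of 2,500 to 6,000 trials per scenario.

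| w | Chance of wrongly meeting the goal | Rise in estimate (points) |
|---|---|---|
| 0 | 1.8–2.1% | – |
| 2 | 3.0–3.5% | about 0.9 |
| 4 | 4.0–5.5% | 1.4–1.6 |
| 6 | 6.8–8.1% | 2.1–2.5 |

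With withdrawal unrelated to outcome, the rate is about 2.0% for 6 withdrawals and 2.1% for 15, both below 2.5%. For scale, the whole attrition allowance is 150 × 0.10 = 15 subjects.

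**The case against.** A reader might infer that Protocol 13.19 contradicts the SAP's intention-to-treat rule, or that withdrawn subjects drop out of the primary analysis. The documents do not support either. SAP 6.1.3 says who is analysed, not when follow-up may end. Withdrawn subjects stay in the set, contribute data to exit and keep any documented failure. Both texts can be followed at once.

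The plan also has real safeguards:

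- Protocol 17.3.1 and SAP 6.4 set early exits to failure one at a time in a tipping-point analysis. SAP 6.4 substitutes a worst-case analysis when fewer than 5 subjects have missing data, and compares early exits with completers at baseline.
- An independent core lab reads the recordings, so the investigator would have to act before a recurrence is documented.
- An early exit calls for an unscheduled visit with an ECG (Protocol 13.11), although 13.19 says only that the visit should be attempted.
- The Protocol leans towards retention. A missed weekly transmission is not a deviation (13.18), and a late visit is preferred to a missed one (13.10).
- Protocol 15.4 asks for continued follow-up of unresolved procedure- or system-related events after exit.

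Most of this stands and keeps the point minor. What remains is that the tipping-point analysis is only a sensitivity analysis. It orders exits by time rather than reason, states a threshold only for the 40% efficacy goal although SAP 6.4 also intends it for safety, and cannot restore unobserved outcomes. Following known adverse events does not capture new late ones.

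**Conclusion.** The point holds as a minor, preventable weakness in design wording. Two administrative reasons can end observation of a treated, failure-free subject, and the resulting censoring may be informative.

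The increase from about 2% to roughly 3–8% rests wholly on the assumption that every withdrawn subject is a certain failure censored just before documentation, with 2 to 6 such subjects. The documents give no count, and nothing in them suggests that investigators would withdraw subjects selectively. The risk concerns borderline results. At the planned 54%, the illustration meets the efficacy goal either way.

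**What to change.** - **Protocol 13.19:** limit the two named reasons (eligibility not met, inadequate compliance) to subjects in whom the catheter has not been inserted. State that treated subjects are not exited for these reasons and stay in scheduled follow-up to 12 months. Leave the exits for consent withdrawal, loss to follow-up, medical justification, and study or center closure unchanged.
- **SAP 6.1.1:** reconcile the eligibility condition with 6.1.2, 6.1.3 and 6.2.2.5, so that it is clear that treated ineligible subjects are in the primary analysis.
- **Analysis:** no new efficacy sensitivity analysis is needed, because SAP 6.4 already covers it. At most, add the reason for exit to the tipping-point table.

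The cost is a wording change in each document and continued follow-up of a few subjects already in the visit schedule. The change concerns observation only and alters no treatment rule.

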14.1. Potential Risks

Medtronic follows rigorous Quality Assurance and Control procedures throughout the life of a product, from the business analysis phase through development, market release, and post-market surveillance. The residual risks associated with the Arctic Front Advance and Freezor *MAX* Cardiac CryoAblation Catheters have been found to be acceptable and have been mitigated to the fullest extent possible. The potential benefits related to the use of the Arctic Front Advance and Freezor *MAX* Cardiac CryoAblation Catheters have been determined to outweigh any potential risks. Neither device has been recalled.

There are potential risks and side effects associated with ablation procedures. The Investigator shall describe risks in further detail when asked by the subject. The risks must be continuously monitored, assessed and documented by the Investigator. The current Arctic Front Advance Instructions for Use should be referenced as the list below may be updated during the course of the study. Possible additional risks for participating in the study include the following (although others are possible):

- Anemia-deficiency of red blood cells or of hemoglobin in the blood resulting in weariness
- Anxiety-a feeling of worry, nervousness, or unease
- Back pain-pain felt in the lower or upper back
- Bronchitis, cough, pneumonia-inflammation of the lungs can be caused by a virus or bacteria
- Cardiac tamponade-pressure on the heart as a result of fluid collecting in the sac surrounding the heart
- Cardiopulmonary arrest-cessation of blood circulation and/or respiration due to dysfunction of the heart and/or lungs
- Chest discomfort/pain/pressure-includes a range of feeling from sharp stabbing to dull ache in the chest
- Cold feeling-having a low or inadequate temperature
- Complications associated with contrast agents-adverse effects of contrast agents used during the procedure (e.g. allergic reaction or radio contrast nephropathy)
- Complications associated with medications commonly utilized during the procedure-known risks of medications commonly used during the procedure (e.g. narcotics, anxiolytics, other pain medications, anti-vasospasm agents)
- Complications at catheter insertion site in the groin:
 - AV fistula-an abnormal connection between an artery and a vein (i.e., cause by needle insertion through the femoral artery and vein)
 - Hematoma/Bruising/Ecchymosis-a collection of blood in the tissue surrounding the catheter insertion site

- Infection-localized redness, heat swelling and pain at the catheter insertion site
- Pain-discomfort at the catheter insertion site that can range from mild to severe
- Pseudoaneurysm-a collection of blood in the tissue surrounding the catheter insertion site due to ongoing leaking of blood from a blood vessel
- Significant bleeding-blood loss from the catheter insertion site requiring surgery or transfusion of 2 or more units of packed red blood cells (PRBCs)
- Coronary artery spasm, vasospasm-constriction of a blood vessel
- Death-a complication or deterioration of health ultimately leading to a patient's death
- Diarrhea-feces are discharged from the bowels frequently and in a liquid form
- Difficulty swallowing-narrowing of the esophagus
- Digestive discomfort-pain in the abdomen
- Dissection of a blood vessel-tear within the wall of a blood vessel
- Dizziness, lightheadedness-feeling faint, woozy, weak or unsteady
- Embolism-formation and dislodgement of a blood clot (thrombus) or dislodgement of cholesterol/plaque within the blood vessel, which travels downstream into small vessels, blocking blood flow and causing temporary or permanent damage to organs distal to blockage. Emboli are known to cause myocardial infarction, transient ischemic attack, stroke/cardiovascular accident, blurred vision, visual changes, paralysis, paresis, or kidney damage, peripheral ischemia and may ultimately lead to incapacitation or death. Symptomatic and non-symptomatic.
- Endocarditis –inflammation of the inner surface of the heart
- Esophageal injury –damage to your swallowing tube, atrio-esophageal fistula - abnormal passageway between the heart and esophagus, hematemesis (vomiting blood)
- Fatigue-extreme tiredness
- Fever-abnormally high body temperature
- Headache-pain in the head
- Heart rhythm disturbances-disruption of normal heart rate or rhythm e.g. atrial flutter, tachycardia, bradycardia, heart block
- Hemothorax-collection of blood around the lungs
- Hiccups-involuntary spasm of the diaphragm and respiratory organs
- Hypertension-high blood pressure
- Hypotension-low blood pressure
- Hypoxia-deficiency in the amount of oxygen reaching the tissues

- Infection (e.g. pericarditis-infection of the sac that surrounds the heart, sepsis-infection throughout the body, urinary-infection of the urinary system)
- Injury to lung- (e.g. bronchial lesion, hemoptysis, constriction, pulmonary hemorrhage, bronchia fistula)
- Mild skin discomfort or irritation-redness sensitivity of the skin cause during or after the procedures (e.g. electrodes used with the ECG and Holter recorder might cause mild skin discomfort or irritation or some skin discomfort following electrode removal or tape removal).
- Nausea-a sensation of unease and discomfort in the upper stomach with an urge to vomit
- Perforation of a blood vessel or cardiac tissue-unintended puncture through the wall of a blood vessel or cardiac tissue
- Pericardial effusion- fluid collecting in the sac that surrounds the heart
- Nerve injury e.g. damage to the phrenic nerve that controls breathing
- Pleural effusion-collection of extra fluid around the lungs
- Pulmonary edema-excess fluid in the lungs
- Pulmonary hypertension-high blood pressure that affects the arteries in the lungs and the right side of the heart
- Pulmonary vein hematoma-trauma to the pulmonary vein
- Pulmonary vein stenosis-blockage in the blood vessels takes blood from the lungs to the heart
- Pneumothorax-collapsed lung
- Renal dysfunction-kidneys fail to adequately filter waste products from the blood
- Bleeding e.g. bleeding into the retroperitoneal space
- Right sided heart failure-right side of the heart is not pumping blood to the lung normally
- Shivering-body shaking
- Shortness of breath-difficulty breathing
- ST elevation-the ST segment of an ECG is abnormally high above the baseline
- Sore throat-pain in the throat
- Vagal nerve injury (e.g. gastroparesis-delayed gastric emptying)
- Vascular complications requiring surgery-damage to an artery (e.g. femoral) or vein requiring surgical repair
- Vasovagal reaction-reflex of the involuntary nervous system that causes the heart to slow down and blood pressure drops
- Visual changes (e.g. blurred vision)

- Vomiting-forceful expulsion of stomach contents through the mouth and/or nose

